3.7. Visit Windows

3.7.1. Definition of Study Day

Study day is the day relative to the date of the first dose of study drug. Study Day 1 will be defined as the day of first dose of study drug administration.

Study day will be calculated from the date of first dose of study drug administration and derived as follows:

- For postdose study days: Assessment Date – First Dose Date + 1
- For days prior to the first dose: Assessment Date – First Dose Date

The last dose date for an individual study drug will be the end date on study drug administration eCRF for the record where the “subject permanently discontinued” flag is ‘Yes’. The last dose date will be defined as the maximum of the last dose dates of individual study drugs in a treatment group.

If there are subjects for whom the date of last study drug is unknown due to the reason that the subject was lost to follow-up and not able to be contacted, the date of last dose will be estimated using the maximum of nonmissing study drug start or stop dates, visit dates and laboratory collection dates (posttreatment visits and unscheduled visits are not included).

3.7.2. Analysis Windows

Subject visits might not occur on protocol-specified days. Therefore, for the purpose of analysis, observations will be assigned to analysis windows. In general, the baseline value will be the last nonmissing value on or prior to the first dose date of study drug.

Safety laboratory data, HCV RNA, vital signs, height and weight, FibroScan, and Fibrotest, collected up to the last dose date + 3 days are considered to be on-treatment data. The analysis windows for on-treatment HCV RNA, vital signs, height and weight, and safety laboratory data are provided in [Table 3-1](#).

Table 3-1. Analysis Windows for On-treatment HCV RNA, Vital Signs, Height and Weight, Fibrotest ^a, and Safety Laboratory Data

Nominal Visit	Nominal Day	Lower Limit	Upper Limit
Baseline	1	(none)	1
Week 1	7	2	11
Week 4	28	12	42
Week 8	56	43	70
Week 12	84	71	≥85

^a Analysis windows for coagulation parameters and Fibrotest are only defined for Baseline and Week 12.

^b FibroScan is collected at screening, posttreatment week 12 and posttreatment week 24.

Safety laboratory data, HCV RNA, vital signs, height and weight, FibroScan, and Fibrotest, collected after the last dose date + 3 days will be assigned to the posttreatment follow-up (FU) visits. Visit windows will be calculated from the last dose date (ie, FU Day = collection date minus the last dose date) as shown in [Table 3-2](#).

Table 3-2. Analysis Windows for Posttreatment HCV RNA, Vital Sign, Height and Weight, FibroScan, Fibrotest, and Safety Laboratory Data

Nominal FU ^a Visit	HCV RNA, Height and Weight, FibroScan and Fibrotest			Vital Signs and Safety Laboratory Data ^b		
	Nominal FU Day	Lower Limit	Upper Limit	Nominal FU Day	Lower Limit	Upper Limit
FU-4 ^c	28	21	69	28	4	30
FU-12	84	70	146	NA	NA	NA
FU-24	168	147	210	NA	NA	NA

^a FU-x visit = posttreatment Week-x follow-up visit.

^b Vital signs and safety labs will only be summarized for the FU-4 visit (up to 30 days after last dose).

^c Doesn't apply to FibroScan and Fibrotest.

3.7.3. Selection of Data in the Event of Multiple Records in an Analysis Window

Depending on the statistical analysis method, single values may be required for each analysis window. For example, change from baseline by visit usually requires a single value, whereas a time-to-event analysis would not require 1 value per analysis window.

If multiple valid nonmissing numeric observations exist in an analysis window, records will be chosen based on the following rules if a single value is needed:

- For baseline, the last available record on or prior to the date of the first dose of study drug will be selected.
- For postbaseline visits:
 - The record closest to the nominal day for that visit will be selected except for HCV RNA posttreatment follow-up visits, for which the latest record in the analysis window will be selected.
 - If there are 2 records that are equidistant from the nominal day, the later record will be selected.
 - If there is more than 1 record on the selected day, the average will be taken, unless otherwise specified.
- If multiple valid nonmissing categorical observations exist in a window, records will be selected as follows:
 - For baseline, the last available record on or prior to the date of the first dose of study drug will be selected. If there are multiple records with the same time or no time recorded on the same day, the value with the lowest severity will be selected (eg, normal will be selected over abnormal).
 - For postbaseline visits, follow the same rules described above for postbaseline numeric observations, except that if there are multiple records on the same day, the most conservative value will be selected (eg, abnormal will be selected over normal).

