1. INTRODUCTION

1.1. Background

Hepatitis C virus (HCV) is responsible for a large proportion of chronic liver disease worldwide and accounts for 70% of cases of chronic hepatitis in industrialized countries. The global prevalence of chronic hepatitis C is estimated to average 3% {[Esteban 2008](#)}. In Egypt, it is estimated that approximately 15% of the population has been infected with chronic hepatitis C, with genotype 4 accounting for approximately 90% of the infections and genotype 1 for the remainder {[Nakano 2012](#)}, {[Ray 2000](#)}. The proportion of children in Egypt with HCV antibodies was found to be 4% in those aged 15 to 19 years in a 2008 national population survey {[El-Zanaty 2009](#)} while earlier studies found 3% and 9% of screened subjects who were 19 years of age or younger had HCV antibodies {[El-Raziky 2007](#)}. Reports from other countries indicate the natural history of chronic HCV in children is relatively benign, but approximately 4% to 6% have evidence of advanced fibrosis or cirrhosis and some children eventually require liver transplantation for end-stage liver disease as a consequence of HCV infection {[Hu 2010](#)}.

Chronic hepatitis C is highly prevalent in Egyptian children receiving cancer chemotherapy or following allogeneic bone-marrow transplantation. {[El-Sayed 2011](#)}, {[El-Sayed 2004](#)} In 1 study, 33 of 100 children with cancer at 2 centers in Egypt were HCV RNA positive. {[Sharaf-Eldeen 2007](#)} The progression of HCV-related liver disease in this population may be rapid and may be the main cause of death in Egyptian patients with allogeneic bone marrow transplantation {[El-Sayed 2004](#)}. Patients also may experience a flare in their HCV while receiving immunosuppressive chemotherapy; HCV flare, or “reactivation”, has been defined as an increase of ALT to >3x baseline level and/or increase of HCV RNA by 1 log₁₀ IU/mL {[Mahale 2012](#)}. HCV flares were found to have resulted in interruptions of cancer chemotherapy in approximately half of HCV-infected adult patients in a retrospective study by Mahale et al {[Hu 1996](#)}.

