6.3. Post-treatment Assessments (\pm 5 days)

All subjects will complete the Post-Treatment Week 4, 12 and 24 visits, regardless of treatment duration.

Assessments at the Post-Treatment Week 4 visit include:

- Obtain height and body weight
- Symptom directed PE and VS
- Adverse events and concomitant medications
- Blood samples for clinical chemistry and hematology including APRI calculation, HCV RNA, HBV DNA only in subjects HBVAb positive at Screening, PPD
- Urine sample for pregnancy testing (females of childbearing potential)
- Pregnancy prevention counseling, if applicable

Assessments at the Post-Treatment Week 12 and 24 visit include:

- Collect any serious adverse events
- Obtain height and body weight
- For those who achieved SVR at the preceding visit (ie, achieved SVR4 or SVR12): Collect blood samples for HCV RNA PPD
- Collect blood samples for Fibrotest PPD
- Perform Fibroscan

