6.6. End of Study

Subjects are considered to have completed the study after the Post-Treatment Week 24 follow-up visit, regardless of treatment duration and early study drug discontinuation.

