7.3.3. Serious Adverse Events

All SAEs, regardless of cause or relationship, that occur after the subject first consents to participate in the study (ie, signing the informed consent) and throughout the duration of the study, including the protocol-required post treatment follow-up period, must be reported to the eCRF database and Gilead Drug Safety and Public Health (DSPH) as instructed. This also includes any SAEs resulting from protocol-associated procedures performed after informed consent is signed.

Any SAEs and deaths that occur after the post treatment follow-up visit but within 30 days of the last dose of study drug, regardless of causality, should also be reported.

Investigators are not obligated to actively seek SAEs after the protocol defined follow-up period. However, if the investigator learns of any SAEs that occur after study participation has concluded and the event is deemed relevant to the use of study drug, he/she should promptly document and report the event to Gilead DSPH.

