Appendix Table 2. Post-Treatment Study Visits

	4 Weeks Post-Treatment (±5 days)	12 Weeks Post-Treatment ^a (±5 days)	24 Weeks Post-Treatment (±5 days)
Clinical Assessments			
Symptom-directed PE	X		
Height and Weight	X	X	X
Vital Signs	X		
AEs	X	X ^a	X ^a
Concomitant Medications	X		
Fibrosis assessment ^b		X	X
Pregnancy prevention counseling ^c	X		
Laboratory Assessments			
Hematology and Blood Chemistry	X		X
APRI Calculation	X		
HCV RNA	X	X	X
HBV DNA ^d	X	X	X
PPD			
Urine Pregnancy Test ^f	X		

a All SAEs, including deaths, regardless of cause or relationship, must be reported after patient signs the informed consent through the end of the study

b Fibroscan and Fibrotest

c If applicable

d HBV DNA testing done only when subjects are HBcAb positive at Screening

e [Redacted]

f Females of childbearing potential

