7.1.6. Summaries of Adverse Events and Deaths

A brief high-level summary of TEAEs will be provided by the number and percentage of subjects who had the following: any AE; any AE of Grade 3 or above; any AE of Grade 2 or above; any treatment-related AE; any treatment-related AE of Grade 3 or above; any treatment-related AE of Grade 2 or above; any SAE; any treatment-related SAE; any AE that led to premature discontinuation of LDV/SOF (90mg/400mg) or LDV/SOF(22.5mg/100mg); any AE leading to interruption of LDV/SOF (90mg/400mg) or LDV/SOF(22.5mg/100mg). All deaths (including those that are treatment emergent and those that are not treatment emergent) observed during the study will also be summarized and included in this table.

Adverse event summaries will provide the number and percentage of subjects with TEAEs by SOC and PT, based on the Safety Analysis Set as follows:

- All AEs
- AEs of Grade 3 or above
- AEs of Grade 2 or above
- All treatment-related AEs
- Treatment-related AEs of Grade 3 or above
- Treatment-related AEs of Grade 2 or above
- All SAEs
- All treatment-related SAEs
- All AEs leading to premature discontinuation of LDV/SOF
- Deaths

Multiple events will be counted only once per subject in each summary. Adverse events will be summarized and listed first in alphabetic order of SOC and then by PT in order of descending incidence of the pooled treatment groups within each SOC. In summaries by severity grade, the most severe grade will be used for those AEs that occurred more than once in an individual subject during the study.

In addition to the above summary tables, TEAEs will be summarized by PT only, in order of descending incidence for:

- AEs of Grade 3 or above
- All treatment-related AEs
- All SAEs
- AEs leading to premature discontinuation of LDV/SOF

In addition to the by-treatment summaries described above, data listings will be provided for the following:

- All AEs (with a variable indicating whether the event is treatment emergent)
- AEs of Grade 3 or above
- SAEs
- Deaths
- AEs leading to premature discontinuation of LDV/SOF

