Appendix Table 2. Post-Treatment Study Visits

	4 Weeks Post-Treatment (±5 days)	12 Weeks Post-Treatment ^a (±5 days)	24 Weeks Post-Treatment (±5 days)
Clinical Assessments			
Symptom-directed PE	X		
Height and Weight	X	X	X
Vital Signs	X		
AEs	X	X ^a	X ^a
Concomitant Medications	X		
Fibrosis assessment ^b		X	X
Pregnancy prevention counseling ^c	X		
Laboratory Assessments			
Hematology and Blood Chemistry	X		X
APRI Calculation	X		
HCV RNA	X	X	X
HBV DNA ^d	X	X	X
PPD			
Urine Pregnancy Test ^f	X		

a All SAEs, including deaths, regardless of cause or relationship, must be reported after patient signs the informed consent through the end of the study

b Fibroscan and Fibrotest

c If applicable

d HBV DNA testing done only when subjects are HBcAb positive at Screening

e [Redacted]

f Females of childbearing potential

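### Non-fatal SAEs that start more than 30 days after last dose, and the post-treatment Week 24 blood tests, reach listings but no summary table

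*SAP*

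**What the plan says.** **Collection.** Under Protocol 7.3.3, SAEs from consent onwards and "throughout the duration of the study, including the protocol-required post treatment follow-up period, must be reported to the eCRF database". Protocol 6.6 fixes the end point: "Subjects are considered to have completed the study after the Post-Treatment Week 24 follow-up visit". The footnote on the Week 12 and Week 24 adverse-event cells of Protocol Appendix Table 2 agrees: "All SAEs, including deaths, regardless of cause or relationship, must be reported after patient signs the informed consent through the end of the study". The same table, repeated in SAP Appendix 1, has a row "Hematology and Blood Chemistry" that is marked at post-treatment Weeks 4 and 24 and blank at Week 12.

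**Reporting.** SAP 7.1.5.1 ends the treatment-emergent period 30 days after study drug is stopped. An event that led to stopping also counts. The SAE rows and tables in SAP 7.1.6 are restricted to treatment-emergent events. SAP 7.2 and 7.2.3 end laboratory summaries, graded abnormalities and their denominators at last dose plus 30 days. Table 3-2 gives safety laboratory data one post-treatment window, days 4 to 30, and enters NA for FU-12 and FU-24. Its footnote b states: "Vital signs and safety labs will only be summarized for the FU-4 visit (up to 30 days after last dose".

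**Exceptions in the SAP.** In the overview table of SAP 7.1.6, "All deaths (including those that are treatment emergent and those that are not treatment emergent) observed during the study will also be summarized". Height, weight, FibroScan and Fibrotest have an FU-24 window of days 147 to 210 in Table 3-2, and SAP 7.3 summarises weight, height and BMI by visit.

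**The concern.** Safety and tolerability form one of the two primary objectives. After day 30 the protocol no longer collects non-serious events (Protocol 7.3.2), so SAEs and the Week 24 bloods are the main safety information from the rest of follow-up. The trial collects or schedules both, yet neither reaches a table.

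The reported SAE percentage will look like a whole-study figure to many readers, although it covers treatment plus 30 days. A first marked laboratory abnormality at Week 24 would not enter the by-visit table or the graded-abnormality table. The SAP already goes past day 30 for deaths, weight and fibrosis measures, so the limit is not a general principle of its reporting.

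**Working it through.** The plan states no figure on this point, so there is none to reproduce. The check is day arithmetic, followed by a comparison of what is scheduled with what is tabulated.

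**Inputs**
- Summary limit: day 30 after last dose (Protocol 8.6; SAP 7.1.5.1, 7.2 and Table 3-2).
- End of follow-up: nominal FU day 168 (SAP Table 3-2), visit tolerance ±5 days (Protocol 6.3).
- Treatment: 12 weeks, or 84 days.
- Post-treatment Week 4 visit: day 28 ±5 (Appendix Table 2).
- Subjects enrolled: 19 (SAP 1.3).

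**SAE coverage, in days**
- Post-treatment days outside the tables: 168 − 30 = 138, and 138 / 168 = 82.1%.
- Over the visit tolerance: (163 − 30) / 163 = 81.6%, and (173 − 30) / 173 = 82.7%.
- From first dose: 84 + 168 = 252 days in all. Inside the tables are 84 + 30 = 114 days, or 114 / 252 = 45.2%. Outside are 138 / 252 = 54.8%.

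**Laboratory coverage, in visits**
- A subject who completes treatment has five scheduled post-baseline haematology and chemistry draws: Weeks 4, 8 and 12, then post-treatment Weeks 4 and 24.
- Four of the five have a summary window. The Week 24 draw does not.

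**Week 4 window**
- Permitted visit days are 28 − 5 = 23 to 28 + 5 = 33, which is 11 days.
- The SAP window ends at day 30, so days 31, 32 and 33 are on schedule but untabulated: 3 / 11 = 27% of the permitted days.

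**Where the late data do appear**
- SAP 7.1.6 lists all adverse events with a treatment-emergent flag, and lists SAEs and deaths separately.
- SAP 7.2 lists laboratory results by subject and visit, and flags out-of-range or graded values.
- The Grade 3 or above listing in SAP 7.2.3.2 shows an analyte's results from the whole study, but a treatment-emergent abnormality is what puts a subject in it. A first Grade 3 value at Week 24 would not. It would appear only as a flagged line in the full listing.

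**Is the Week 24 draw settled?** No. In Protocol 6.3, the list headed "Assessments at the Post-Treatment Week 12 and 24 visit include" covers SAEs, height and weight, HCV RNA, Fibrotest and Fibroscan. Its readable part does not name haematology or chemistry, which Protocol 6.3 names only at post-treatment Week 4. Appendix Table 2 marks them at Week 24. Some words in that list are blacked out, so the conflict is between the readable text and the table.

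**The case against.** The strongest reply is that the limit was specified in advance and applied evenly. Protocol 8.2.1.2, 8.6, 8.6.2 and 8.6.3 set last dose plus 30 days, and the SAP follows them. A reader might infer that the SAP contradicts the protocol. It does not: collecting data for longer than they are tabulated is not an inconsistency. This part of the reply stands in full.

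Second, nothing is lost. With 19 subjects, every late SAE and every Week 24 result can be read line by line. This stands as mitigation, but a listing gives no count or percentage for the report to quote.

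Third, calendar days are a poor measure for laboratory data that are collected by visit. This also stands. The 82% describes SAE follow-up time. For laboratory data the gap is one scheduled draw in five, and whether that draw was required is itself unclear.

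Fourth, in a single-arm trial in children on chemotherapy, late SAEs say little about the study drug. That is a reason to label such rows, but it does not justify leaving them out: the SAP tabulates late deaths despite the same difficulty.

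Finally, the exploratory endpoints and their methods are blacked out in both documents. An analysis of late laboratory data could sit there, so the point is limited to the readable text.

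**Conclusion.** The point holds as a reporting gap of modest weight. Non-fatal SAEs with onset beyond day 30 and the Week 24 haematology and chemistry have no planned table in the readable text. The limit leaves 138 of 168 nominal post-treatment days (82%; 81.6% to 82.7% over the visit tolerance) outside the SAE tables and one scheduled laboratory visit outside the by-visit tables. It also drops Week 4 samples taken on days 31 to 33. These figures assume nominal visit timing, a full 12 weeks of treatment, and a Week 24 draw as in Appendix Table 2.

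Two stronger readings are not supported:
- A reader might infer that deaths are the only safety data tabulated after day 30. SAP 7.3 and Table 3-2 show otherwise for weight, height and BMI.
- A reader might infer that the plan hides hepatic flares following virologic relapse, because Protocol 1.1 says that flare "has been defined as an increase of ALT to >3x baseline level and/or increase of HCV RNA by 1 log". That section describes flare during immunosuppressive chemotherapy and says nothing about flare after relapse. HCV RNA at FU-12 and FU-24, and relapse itself, are tabulated under SAP 6.2.

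**What to change.** 1. **SAP 7.1.6.** Add one row to the overview table: subjects with any SAE from first dose through post-treatment Week 24, placed beside the treatment-emergent SAE row and labelled as not limited to treatment-emergent events.
2. **Week 24 bloods.** Reconcile Protocol 6.3 with Appendix Table 2. Where samples were drawn, give safety laboratory data an FU-24 window of days 147 to 210 in Table 3-2, as HCV RNA already has, and summarise them by visit as post-treatment data.
3. **Week 4 bloods.** Extend the FU-4 laboratory window for by-visit tables to at least day 33, so that visits within the protocol's own tolerance are kept.
4. **Consistency.** Amend footnote b and the day-30 sentence in SAP 7.2 to allow these by-visit rows, and record the additions in SAP 7.6, which now reports no departures. Leave the 30-day treatment-emergent definition, and the graded-abnormality tables that rest on it, unchanged.

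The cost is SAP wording and a few table rows from data that are collected or scheduled, with no new procedures. The drawback is that late events and blood values are confounded by chemotherapy and the underlying cancer, so the added rows must say that they are post-treatment and should not be read as drug effects.

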4. SUBJECT DISPOSITION

4.1. Subject Enrollment and Disposition

A summary of subject disposition will be provided. This summary will present the number of subjects screened, the number of subjects enrolled, and the number and percentage of subjects in each of the categories listed below. For the “Treated” category, the denominator for the percentage calculation will be the total number of subjects enrolled for each column. For all other categories, the denominator for the percentage calculation will be the total number of subjects in the Safety Analysis Set for each column.

- Treated (Safety Analysis Set)
- In FAS
- Completed study treatment
- Did not complete study treatment with reason for premature discontinuation of study treatment
- Completed the study (completed posttreatment Week 24 visit)
- Did not complete the study with reason for premature discontinuation of study

Among subjects who completed study treatment and who discontinued study treatment, the number and percentage of subjects will be summarized for:

- Who had no HCV posttreatment Week 4 assessment and thereafter (No HCV FU-4 and thereafter)
- Who had HCV posttreatment Week 4 assessment but no HCV posttreatment Week 12 assessment and thereafter (With HCV FU-4 but No FU-12 and thereafter)

If a subject did not have any HCV RNA assessment ≥ 21 days after the last dose of any study drug (ie, lower bound of FU-4 visit for HCV RNA data), the subject is categorized as having “No HCV FU-4 and thereafter”. If a subject had the HCV FU-4 assessment but did not have any HCV RNA assessment ≥ 70 days after the last dose of any study drug (ie, lower bound of FU-12 visit for HCV RNA data), the subject is categorized as having “With HCV FU-4 but No FU-12 and thereafter”.

In addition, the total number of subjects who were enrolled in the study, and the number and percentage of subjects in each of the disposition categories listed above will be displayed in a flowchart.

The following by-subject listings will be provided by subject ID number in ascending order to support the above summary tables:

-
- Disposition for subjects who complete study treatment and study
 - Disposition for subjects who did not complete study treatment and/or study with reasons for premature discontinuation of study drug and/or study
 - Lot number and kit ID

